## 13.0 Study Timeline (optional)

	Pre-Screening	Visit 1	Visit 2	Visit 3	Six week Follow up
Estimated time requirement of visit					
Data Collection					
Study Procedure 1					
Study Procedure 2					
Study Procedure 3					
Phone Call Questionnaire					

## 14.0 ClinicalTrials.gov Information

**Directions: If this study has been registered on ClinicalTrials.gov, provide the ClinicalTrials.gov identifier and the investigator/sponsor responsible for registering. If this study has not been registered on ClinicalTrials.gov, provide the rationale as to why and if/when it will be. If it does not meet the requirement for being registered on ClinicalTrials.gov, please state that.**

Unique Protocol ID: STUDY20230876.

## 15.0 List of Data to be Collected

1. *Indicate what identifiers you will collect*

- Name
- Address (e.g., Zip code, other geographical designation, etc.)
- Dates related to an individual (e.g., Date of admission, birth, surgery, etc.)
- Telephone number
- Fax number
- Email address
- Social security number
- Medical record number
- Health plan beneficiary number
- Account number
- Certificate/license number
- Any vehicle or other device serial
- Device identifiers or serial numbers
- Web URL
- Internet protocol (IP) address
- Finger or voice prints (*includes audio recordings*)
- Photographic images (*includes video recordings*)
- Other: Any characteristic that would uniquely identify the individual  
If other, please explain: [Click here to enter text.](#)

2. List all other data to be collected for the research study. Attach all data collection tools on the Local Site Documents page of the SpartaIRB smart form (Other Attachments). Baseline, Follow Up 1, and Follow Up 2 Surveys; Qualitative interviews (recordings and transcripts); Utilization of NeuViCare App including logins, completion of activities, receipt of text messages, community forum posts, and AI prompts (de-identified; includes non-study participants); Intervention fidelity, including selected CONFIDENCE session recordings; Characteristics of study participants and non-study participants (USC FCSC Eventbrite registration); intervention attendance; Study adverse events; Study retention

## 16.0 Online Data Collection

- We will not collect data through an online platform.

1. List the online platform to be used. The preferred platforms are REDCap and Qualtrics, as these provide good data security and have options for collecting data without individually identifiable information.
 

All survey data will be collected through REDCap. Qualitative interview data will be collected on an institutional Zoom account and recorded. Eventbrite data will also be downloaded on registrants, regardless of study participation. Eventbrite data, also collected in the previous CONFIDENCE study, includes information such as demographics information to help us understand the characteristics of those who participate in the CONFIDENCE program when delivered in a community setting. Finally, app utilization data in the NeuViCare program will be stored in a dashboard and made accessible to the study team by individual password protected accounts.
2. If your intent is to collect the data without identifiers linked to an individual (including IP addresses), describe how you will ensure that no identifiable information will be associated with the data.
  - Qualtrics: enable Anonymize Responses setting (removes IP addresses and location data)
  - REDCap: use of the Public Survey Link
  - REDCap: use of a Participant List without a Participant Identifier field
 

*(Note: this does maintain a connection between the data and the individual, but it is only accessible to REDCap support personnel and not the researchers. Data collected in this manner should not be referred to as anonymous, but rather as data that is deidentified to the researchers).*
  - Other: [Click here to enter text.](#)

## 17.0 Data Analysis Plan

**Directions: Describe the data analysis plan, including any statistical procedures. If applicable, provide a power analysis, and study/safety endpoints.**

**Outcome measures.** *Resourcefulness (primary outcome).* Resourcefulness skills help family caregivers lower material out-of-pocket costs through identification of community resources and alternative ways of managing costs. This will be measured using Resourcefulness Scale, a 28-item scale used to measure potential and social resourcefulness (alpha=0.83; range: 0 to 140). *Self-efficacy (second primary outcome)* is measured using the Caregiver Self-Efficacy Scale. This 8-item scale combines domains of self-efficacy (e.g., managing behavioral symptoms, accessing respite, and controlling upsetting thoughts. It demonstrates high reliability (alpha=0.89) and good test-retest reliability (0.73). Scores range from 8 (lowest) to 80 (highest). *Financial strain (secondary outcome).* Interventions to reduce caregiver financial strain are needed across multiple levels, individual-level behavioral interventions are needed given the slow pace of policy change to promote caregiver's financial security. This will be primarily measured using the 11-item Comprehensive Score for Financial Toxicity (COST) Scale, which has been modified from the cancer field, which demonstrates validity and reliability (a=0.91; range: 0 to 44). We will also use a secondary measure of psychological financial strain that was used in the initial CONFIDENCE study. (See NCT05292248 for details on this measure.) *Community Resource Access (ancillary outcome).* This author made item asks about caregivers'

access to community resources that may reduce the costs of caregiving. We will assess whether or not caregiver accessed 1 or more new community resources since beginning CONFIDENCE.

**Outcome Analysis.** Scores for resourcefulness, self-efficacy, and financial strain will be analyzed using t-test analyses, where we will compare baseline scores to scores from each follow-up survey. If there is a p-value  $<0.05$ , this indicates that there was a statistically significant difference between scores. Mean scores and standard deviation for all scores on each scale will be also examined. (We will use descriptive statistics alone to assess whether or not a caregiver accessed new resources following program participation.)

**Satisfaction surveys.** To analyze Likert responses to satisfaction surveys, a percentage for each response will be provided. Each item will be compared to items collected for the initial CONFIDENCE study, as well as scores for items of CONFIDENCE between Spanish and English intervention.

**Attendance.** We will report the average number of sessions attended (range 0 to 4) and the standard deviation. Comparison on the number of sessions attended will be compared between the English and the Spanish sessions as well as between the earlier and current version of CONFIDENCE in the form of percentages to allow us to draw preliminary comparisons, given the different number of possible sessions to attend (3 vs. 5). The average number of sessions will be calculated both with and without accounting for make-up sessions. (i.e., giving credit for attendance in Session 1 if the caregiver attended the makeup session for this lesson.)

**App Utilization.** Usage data from NeuViCare™ Care and Resources Advisors will be reported in aggregate Individual-level data will be collected on the average number of text received, average interactions on the Community Hub, and average number of practice activities completed on NeuViCare.

**Fidelity.** Fidelity reports will be evaluated using total scores averaged across all CONFIDENCE sessions observed. Sub scores will be reported for adherence to the facilitator guide, participant experience, and quality of delivery. These will be reported separately for English and Spanish participants by using a percentage, as well as means and standards of deviation, to examine variability.

**Qualitative interviews.** Qualitative interviews will be transcribed verbatim, and for the ones conducted in Spanish, they will be previously translated. Transcription and translation of interviews conducted in Spanish will be by ASTA-USA. English Transcriptions will be done by GMR. A preliminary code book will be developed by at least two research members and will be refined prior to applying codes to the remaining interviews. At least two coders will analyze each transcript independently and will meet to compare the codes. The second round of coding will be conducted to integrate new codes if needed.

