## 5.0 Number of Research Participants

**Directions: Indicate the target number of research participants to be accrued locally, and, if this is a multi-site study, indicate the total number of research participants to be accrued across all sites.**

**Example language that can be used:** *We will enroll 25 subjects at CWRU and plan to enroll 150 subjects study wide.* We will recruit 42 family caregivers to account for the anticipated 20% attrition before and after participation in CONFIDENCE 2. Moreover, at least 12 participants will complete qualitative interviews.

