**Recruitment strategy.** Caregivers will primarily be recruited from the USC FCSC by sending information about CONFIDENCE via email blast, as well as individual email invitations and follow-up calls sent to participants who are likely to be eligible for the study. The USC FCSC may also advertise this program via social media channels and with community partners, as they would any program they offer to the community. Caregivers may also learn about the study on the Alzheimer’s Association TrialMatch

site.

**Enrollment and consenting.** Participants who register on Eventbrite and are interested in learning about the study will receive up to four calls and emails by a study team member to learn more about the study. If interested in participating, eligibility screening and a review of the study consent information will be conducted by phone with the PI or a trained study team member. (Participants may complete the screening process online, but are asked to complete a telephone follow up where they will be asked the screening item about the Global Deterioration Scale and other questions they did not respond to.) Participants will then be sent an email with a REDCap consent form to review and signature. Total enrollment and consenting time is estimated to take up to 1 hour.

**Survey administration.** Once enrolled, participants will receive the baseline survey up to 3 weeks before their first CONFIDENCE session by email, which includes questions about spending on out-of-pocket care costs, financial strain, resourcefulness, self-efficacy, and information about the caregiving context and use of supports. The first follow-up survey will be sent immediately post-intervention (i.e., within 1 week). A second follow-up survey will be sent two months following intervention completion to understand the maintenance of outcomes. We estimate follow up surveys take about 30 to 45 minutes to complete.

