## 23.0 Withdrawal of Research Participants

**Directions: Describe the anticipated circumstances under which research participants will be withdrawn from the research without their consent. Also include the procedures that will be followed when a research participant withdraws or are withdrawn from the research, including partial withdrawal from procedures with continued data collection.**

Participants will be removed from the study if the study team believes the participant is fraudulent (e.g., inconsistencies in study information provided), submits surveys that are excessively incomplete (e.g., more than 50% of responses are missing), or is no longer eligible (e.g., care recipient passes away). Participants will be notified by email if they are removed from the study. Participants may continue to participate in the study to complete the second follow up survey, even if the first follow up survey is not complete. The research team will retain study data for participants who are withdrawn or lost to follow up, unless it is specifically requested by the participant that data be removed prior to de-identification.

- N/A

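### Section 17.0's separate t-tests name no analysis set or missing-data method, so completer estimates of change may be biased and the two follow-ups may rest on partly different people

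*Combined protocol and SAP*

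**What the plan says.** Section 17.0 (Outcome Analysis) uses t-tests in which "we will compare baseline scores to scores from each follow-up survey", judges each at p<0.05, and adds means and standard deviations. It does not say that the tests are paired, who is analysed, or what happens to missing surveys or items.

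Section 12.0 (Survey administration) gives the later survey its purpose: "A second follow-up survey will be sent two months following intervention completion to understand the maintenance of outcomes".

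Section 5.0 recruits 42 caregivers "to account for the anticipated 20% attrition before and after participation in CONFIDENCE 2".

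Section 23.0 holds the rules that decide whose data exist:
- Suspected fraud: "Participants will be removed from the study if the study team believes the participant is fraudulent".
- Blank surveys: removal of anyone who "submits surveys that are excessively incomplete (e.g., more than 50% of responses are missing".
- Lost eligibility: "or is no longer eligible (e.g., care recipient passes away".
- Intermittent response: a person may "complete the second follow up survey, even if the first follow up survey is not complete".
- Retention: "The research team will retain study data for participants who are withdrawn or lost to follow up", unless the person asks for deletion.

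Section 20.0 allows questions to be skipped. Section 15.0 lists retention among the data collected, and Section 28.0 has a six-monthly report on the characteristics of enrolled and retained participants. Neither is tied to the outcome analysis.

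**The concern.** The plan anticipates missing surveys, and its own rules create more, but the outcome analysis is written as if every survey came back. A paired t-test drops anyone without that follow-up. If the people who return differ in their scores from those who do not, the completers' mean change is not the mean change of those enrolled.

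Two further consequences follow. Maintenance would be read from two separate comparisons with baseline, each on its own set of returners, with no direct contrast between the follow-ups. And Section 23.0 retains the records of withdrawn people without saying whether they are analysed, so that choice could be made after the results are seen.

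**Working it through.** **1. The plan's own figure.** 42 × 0.8 = 33.6, so about 34 returns if 20% is the loss at each follow-up. Working back, 33 / 0.8 = 41.25, which rounds up to 42. But no completer target, effect size or power is given, so 42 can be neither confirmed nor refuted. Section 5.0 could also mean 20% at each of two stages: 42 × 0.8 × 0.8 = 26.9, about 27 returns (36% loss).

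**2. Overlap of the two follow-up samples.** With 34 returns at each, 8 are missing at each. The fewest people in both is 42 − 8 − 8 = 26; the most is 34. On the two-stage reading it is 42 − 15 − 15 = 12, up to 27.

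**3. Bias of the paired completer estimate when return depends on baseline.** Let b be the slope of follow-up on baseline, b = correlation × (follow-up SD / baseline SD), and m the returners' mean baseline minus everyone's. Then bias = (b − 1) × m.
- Assume equal SDs, so b equals the correlation. The documents give no pre/post correlation. I take 0.50 (assumed) to 0.73 (Section 17.0's test-retest figure, for self-efficacy only).
- With 80% return and odds of return doubling per SD of baseline, large-sample simulation gives m of about 0.13 SD.
- Correlation 0.50: (0.50 − 1) × 0.13 = −0.065 SD. Correlation 0.73: (0.73 − 1) × 0.13 = −0.035 SD.
- The sign depends on b. At b = 1 the bias is zero, and above 1 it reverses. At correlation 0.73 that needs an SD ratio above 1 / 0.73 = 1.37; at 0.50, above 2.

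**4. Yardstick.** The standard error of a paired mean change in SD units is √(2(1 − r)/n). With n = 34: √(1.00/34) = 0.171 at r = 0.50 and √(0.54/34) = 0.126 at r = 0.73.

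**5. Simulation, for illustration only.** The settings were 42 people, normal scores with SD 1, true change 0.30 at both follow-ups, correlation 0.50 or 0.73, logistic loss of 20% with slopes 0.5 to 1.5 per SD, and 1,500 runs per setting (Monte Carlo error at most 0.006). The model is maximum likelihood on all three visits with unstructured covariance. Estimated 2-month change (truth 0.30):

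| Loss depends on | Paired completers | Model |
|---|---|---|
| Nothing (random) | 0.298-0.302 | 0.297-0.303 |
| Low baseline score | 0.194-0.273 | 0.297-0.307 |
| High baseline score | 0.330-0.411 | 0.295-0.303 |
| Small immediate change (immediate survey complete) | 0.335-0.415 | 0.296-0.305 |
| Unseen 2-month change | 0.373-0.524 | 0.356-0.466 |
| Unseen 2-month score | 0.325-0.413 | 0.341-0.469 |

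When loss depends on seen scores (rows 2 to 4), the paired bias runs from 0.30 − 0.273 = 0.027 to 0.415 − 0.30 = 0.115, that is 0.03-0.12 SD and at most 0.70 of a standard error. At 36% loss it is 0.04-0.20 SD, at most 1.05 standard errors. The model's root-mean-square error at 20% loss is 3-17% below the paired test's in those rows. In the last row it is 2-17% above.

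**6. Maintenance.** In the small-immediate-change row the true difference between follow-ups is zero. The two paired estimates differ by 0.033-0.116 SD, while the model's differ by no more than 0.01.

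**7. Removal rule.** Section 23.0 accepts follow-up 2 from someone whose first follow-up is not complete, yet removes someone whose surveys are largely blank. A person with a largely blank first follow-up meets both rules. If removed, any later survey is lost.

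**The case against.** Pairing is the natural reading. Section 12.0 describes a single-arm pre- and post-test trial, and Sections 12.0 and 18.0 (Confidentiality of Data) describe a study key that links records. That stands, and one added word would settle it. It would still leave the analysis set, the missing-data method and the removal rule open.

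The bias is conditional and modest. This also stands: the upper end needs a strong link between scores and return, and Section 2.0 claims only preliminary efficacy alongside feasibility and acceptability.

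The model is not uniformly better. It does worse than the paired test when loss depends strongly on the unseen score, and interval coverage with small-sample degrees of freedom was not simulated. A stated paired test with numbers per visit, a returner comparison and a sensitivity analysis would be defensible. The model is preferred as the main analysis because it uses every score collected and removes the bias due to seen scores. The paired test stays beside it.

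Maintenance can be judged by whether 2-month scores still differ from baseline, which Section 17.0 tests. True; the direct contrast is an addition, and it guards against reading two differing samples as a trend.

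Section 23.0 speaks of surveys in the plural and gives 50% as an example, so removal after a single blank survey is one reading only. That is why the point is put as data that can be lost.

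**Conclusion.** The concern holds as a gap that should be closed. Separate t-tests with no stated analysis set or missing-data method leave the estimate open to bias if return is related to baseline or immediate scores, and the two follow-up comparisons can rest on partly different people (26 to 34 in common with 34 returns each). The illustrated bias, 0.03-0.12 SD and at most 0.7 of a standard error, rests on equal SDs, correlation 0.50-0.73, 20% loss and an assumed loss mechanism. The removal rule can also discard usable later surveys.

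A reader might infer three stronger things that the documents do not support. One is that an unpaired test is planned: the design and linkage point the other way. Another is that the bias has a known direction, for example that losing low baseline scorers makes a paired test understate change. That needs a follow-up-on-baseline slope below 1, and no follow-up SD is given. The third is that the results will be biased: no loss mechanism is stated, and under random loss the paired estimate is sound.

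**What to change.** **Section 17.0**
- Main analysis: one likelihood-based repeated-measures model per outcome, with baseline, immediate and 2-month scores, visit as a fixed effect, within-person covariance and small-sample degrees of freedom. Use all available scores from eligible, non-fraudulent participants with a baseline score.
- Report change with a 95% confidence interval at each visit, the 2-month minus immediate difference, and the numbers contributing to each visit and to both.
- Keep the t-test, stated as paired, as the completer analysis.
- Compare returners with non-returners at baseline.
- Add one sensitivity analysis for loss that depends on unseen scores, for example assuming no change in those lost.
- State how each scale is scored when items are skipped: its published rule, or a prorating threshold fixed before analysis. The 50% example in Section 23.0 applies to surveys and does not settle this.
- State how scores after loss of eligibility are used.

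**Section 23.0**
- Treat a survey more than 50% blank as missing for that visit and still send the next one. Keep removal for suspected fraud.

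**Cost.** Wording in two sections and slightly more analysis; no new data or visits. The model assumes data are missing at random and can do worse than the paired test if loss depends strongly on unseen scores, which is why the paired test and the sensitivity analysis are kept.

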## 2.0 Objectives

**Directions: Describe the purpose, specific aims or objectives. Be sure to also include the hypothesis being tested.** The overall objective of this project is to test the feasibility, acceptability, and preliminary efficacy on an AI-enhanced psychoeducational intervention to reduce financial strain among Latino/Hispanic family caregivers to people living with dementia (PLWD) by supporting resource access called CONFIDENCE 2. The central hypothesis is that caregivers who participate in the CONFIDENCE intervention will report higher levels of resourcefulness and self-efficacy following participation in the CONFIDENCE intervention that will reduce financial strain among caregivers of PLWD.

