To address the need for programs to reduce financial strain among Latino caregivers, we developed the Confidently Navigating Financial Decisions and Enhancing Financial Wellbeing in Dementia Caregiving (CONFIDENCE) program with support from AARP Foundation from 2020 to 2023. The original version of CONFIDENCE includes a 5-week, group-based psychoeducational intervention delivered by Zoom. Most data for the evaluation of the CONFIDENCE original program have been collected. Initial findings indicate high satisfaction with the program among participants (100% “Agree” or “Strongly Agree” they would recommend the program to other caregivers), but also lower-than-anticipated uptake and adherence. For example, only 51% of caregivers registering for CONFIDENCE at the USC Family Caregiver Support Center attended at least one session. Of those who attended at least one session, average attendance was 3.1 out of 5 sessions. These findings suggest high acceptability but limited feasibility.

The second version of CONFIDENCE aims to build on lessons learned from the original CONFIDENCE program with the goal of improving program feasibility prior to testing the program’s efficacy. To improve uptake and adherence, we have shortened the number of group-based Zoom discussion sessions from 5 to 4 to reduce the time required to participate. Content covered in the sessions removed from the core program will be delivered by asynchronous, technology-driven means. Participating caregivers will have a chance to decide which topics to focus on based on their current needs and will receive informational text messages covering these topics. Caregivers will also have access to a conversational AI assistant (“Keiko”) that will draw from hand-picked and trusted resources to devise answers to questions caregivers may have about topics such as how to find reduced-cost home modifications, how to prepare for retirement, and how to prevent financial scams. To support learning between discussion sessions, NeuViCare also will host a moderated community forum where caregivers can connect with other participating caregivers .

*Please add relevant references at the end of the protocol, not at the end of this section.*

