## 12.0 Study Design/Procedures

### Directions:

- 1) **Describe the overall study design (e.g.: single visit, single-blind, double-blind, non-randomized, randomized, blood draw, investigational drug, device etc.).**
- 2) **Provide a description of all study-related research procedures being performed, including the length of time involved.**
- 3) **Include procedures being performed to monitor research participants for safety or minimize risks.**
- 4) **Describe the source records including medical or educational records, which will be used to collect data about subjects.**
- 5) **Include a description of any device being used to collect data (e.g., eye tracker, step counter). If the device itself is being studied, include additional information in Section 29.**

**Overall design.** A single-arm pre- and post-test clinical trial of the CONFIDENCE intervention will be conducted. This study builds on the original CONFIDENCE study (STUDY20221010), but with a modified version of the intervention and minor updates in data collection protocols to reduce participant burden. Participation will be offered to any caregiver of persons living with dementia nationally who register for the program via the USC Family Caregiver Support Center (USC FCSC) Eventbrite. Study participation is optional. CONFIDENCE will be delivered in English and Spanish, and participants may participate in the study in either language.

**Intervention** The intervention includes participation in four, 1.5 hour group discussion sessions delivered by Family Consultants from the USC Family Caregiver Support Center. Zoom sessions will be attended by other caregivers and will feature vignette-style videos featuring family caregivers as well as peer-learning activities. Between the sessions, caregivers will receive text messages from NeuViCare™ with informational tips and reminders to complete practice exercises. They may also choose to interact with Keiko, the apps conversational AI assistant that generates responses to questions based on sources selected or created by the study team. Caregivers can also participant in a monitored community forum, wherein they will be able to communicate with other caregivers in the program. Participants will be sent instructions on how to register for the NeuViCare App, and will have a dedicated “NeuViCare champion” at the USC FCSC who they can turn to if they need additional support. Total time for intervention participation in 8 to 10 hours over 4 weeks.

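### Does the plan need a primary time point and a rule for combining its two primary outcomes?

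*Combined protocol and SAP*

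**What the plan says.** Section 17.0, under Outcome measures, labels resourcefulness the primary outcome and self-efficacy a second primary outcome. Financial strain is secondary, and access to community resources is ancillary. Under Outcome Analysis the method is a t-test in which "we will compare baseline scores to scores from each follow-up survey". Of a p-value below 0.05 the plan says that "this indicates that there was a statistically significant difference between scores". It also commits to examining means and standard deviations for all scores on each scale.

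Three other places bear on how this is read:

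- **Section 2.0 (Objectives)** sets the aim as feasibility, acceptability and preliminary efficacy. It hypothesises that caregivers "will report higher levels of resourcefulness and self-efficacy following participation", and the same sentence goes on to a reduction in financial strain.
- **Section 3.0 (Background)** describes this second version of the programme as building on the first "with the goal of improving program feasibility prior to testing" efficacy.
- **Section 12.0 (Study Design/Procedures)** states that "A single-arm pre- and post-test clinical trial of the CONFIDENCE intervention will be conducted". It places the first follow-up within 1 week after the intervention and adds: "A second follow-up survey will be sent two months following intervention completion to understand the maintenance of outcomes".

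No section names a primary time point, an either/both rule, a testing order or a multiplicity adjustment.

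**The concern.** Two primary outcomes at two follow-ups make four primary comparisons, each judged at 0.05. With no stated rule, the same data could be presented in opposite ways. Suppose self-efficacy alone improves, with p=0.04, and only at 2 months. That is a positive result if any of the four tests counts. It is negative if the immediate survey is primary, if both outcomes are required, or if resourcefulness must pass first. In a confirmatory trial this would be a real defect, because the error rate attached to the headline claim would be unknown and the rule could be chosen after seeing the data.

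**Working it through.** **Inputs from the documents.** Two primary outcomes, two follow-ups and p<0.05 per comparison (Section 17.0); survey timing (Section 12.0); 42 recruited, with "anticipated 20% attrition before and after participation in CONFIDENCE 2" (Section 5.0).

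**Assumptions.** Paired two-sided tests on change scores, all nulls true for the error rates, 80% power where power is quoted, and the correlations shown. The documents give none of these.

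**1. The plan's own figures.** The only design figure is 42.
- 33/(1 - 0.20) = 41.25, rounded up to 42; 35 x 1.20 = 42 also fits.
- Completers would be 42 x 0.80 = 33.6 (use 33), or 42 x 0.64 = 26.9 (use 26) if 20% is lost twice.
- No completer target, effect size, power or overall alpha is stated. So there is no promised error rate that the four tests could break.

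**2. Error rate if any of the four tests counted.**
- Improvement only, independent: 1 - 0.975^4 = 0.0963.
- Either direction, independent: 1 - 0.95^4 = 0.1855.
- Simulated paired t-tests, n=33, with between-visit and between-outcome correlations from (0.5, 0.3) to (0.9, 0.7): 8.5% down to 5.8% for improvement, and 17.0% down to 11.7% in either direction. At n=26 the ranges are 8.6% to 5.9% and 17.0% to 11.8%.

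The larger figures count deterioration, which would not be reported as success.

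**3. Error rate at the immediate survey only.**
- Either outcome counts, improvement: 1 - 0.975^2 = 0.0494 (4.2-4.8% with outcome correlation 0.7 to 0.3).
- Either outcome counts, either direction: 1 - 0.95^2 = 0.0975 (8.4-9.5%).
- Both required: at most 2.5% for improvement and 5% in either direction.

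For the hypothesised direction, reading the immediate survey as the main one keeps the rate below 5% without adjustment, even if either outcome counts.

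**4. Cost of requiring both outcomes.** Take the effect that gives 80% power for each outcome. Joint power is 0.80 x 0.80 = 0.64 if the outcomes are independent and about 0.71 at correlation 0.7. To restore 80% jointly, the detectable change must rise from 0.50 to 0.55-0.58 SD at n=33, or from 0.57 to 0.63-0.66 SD at n=26. If either outcome were to suffice under Holm, the corresponding change is at most 0.56 SD (n=33) or 0.64 SD (n=26). A fixed order leaves resourcefulness at 80%.

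**5. What happens if the plan is followed as written.** The analyst runs both outcomes at both follow-ups, tabulates means and standard deviations, and reports each p-value for its own comparison. Nothing in that list is chosen after seeing the data. No stopping rule, sample size or progression decision depends on a combined verdict.

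**6. What the text already implies.** A survey meant to show maintenance presupposes a change at the earlier survey, so the immediate survey is the natural main time point. The wording of the hypothesis is a weaker guide. The sentence that joins the two outcomes also includes financial strain, which Section 17.0 makes secondary. It describes a mechanism and does not set a success criterion. The label given to self-efficacy could equally suggest an order of testing.

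**The case for a change.** The best case for a change is that the investigators chose to name primary outcomes and a significance threshold, and so should say what result meets the primary objective. A few sentences would do it, with no new data. Timing adds weight: Section 8.0 plans recruitment from March 2024 to August 2025 and the protocol is dated 5/19/2025, so follow-up data may already exist. The maintenance wording and the hypothesis sentence only hint at an intention; neither is a rule.

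The factual part of this stands. The rule is absent, and a report could stress whichever of the four results looks best. But it could do so only against a declared set of four comparisons, so a reader can see what was passed over. The rest does not lead to one definite change. Requiring both outcomes, testing in a fixed order, Holm, and declaring the tests exploratory are all defensible. The choice turns on what the investigators intended, and no choice alters the comparisons to be run. Nor would any of them address the main limit on inference, which is that a single arm cannot separate an intervention effect from change over time.

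**Conclusion.** No change is needed. The gap is real but is missing detail of a kind that analysts of a single-arm preliminary-efficacy study fill sensibly: report all four comparisons, treat the immediate survey as the main one and the 2-month survey as maintenance. Each p<0.05 is then a valid statement about its own comparison, and no family-wise rate is promised or broken.

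If any of the four tests were taken as success, the chance of a false-positive improvement would be 9.6% under independence and about 5.8-8.6% under the assumed correlations. At the immediate survey alone it is at most 4.9%. These figures assume paired two-sided tests and 26 to 33 completers. The strictest remedy, requiring both outcomes, would lower power from 80% per outcome to about 64-71% for the pair, in a study whose stated priority is feasibility. That is a fair trade-off for the investigators to make, and the plan is not wrong for leaving it unmade.
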